5.0 Study Parameters

5.1 Primary Endpoints

- [¹⁸F]fluciclovine PET/MRI results for primary lesion and regional nodal metastases
- Concordance between [¹⁸F]fluciclovine PET/MRI results and multiparametric prostate MRI results
- Detection of organ-confined disease, regional nodal metastases, extracapsular extension, and seminal vesicle invasion [¹⁸F]fluciclovine PET/MRI in expected frequencies based on risk-predictor models and nomograms

5.2 Secondary Endpoints

- Potential added value in additional metastases detected on [¹⁸F]fluciclovine PET/MRI versus prostate MRI alone
- Use of followup [¹⁸F]fluciclovine-PET/MRI after initiating therapy to confirm initial suspicious findings on the initial pretreatment study

5.3 Exploratory Endpoints

- Use of [¹⁸F]fluciclovine PET/MRI at 3-6 months following initiation of treatment to evaluate response to therapy at the time when serum PSA is routinely checked following treatment initiation
- Correlate disease burden at 3 month follow up with serum PSA values
- Dynamic radiotracer uptake by the primary lesion and if this changes on the posttreatment [¹⁸F]fluciclovine-PET/MRI
- Changes in signal characteristics of primary intraprostatic lesion on posttreatment mpMRI
- Changes in initial treatment plan with added information provided by fluciclovine PET/MRI versus standard-of-care imaging alone

5.4 Study Termination

The study will stop enrolling patients once the target number has been reached.

6.0 Statistical Considerations

6.1 Study Design

This is a prospective pilot trial to determine the potential use of [¹⁸F]fluciclovine PET/MRI in the pretreatment staging and post-therapy follow-up of patients with high-risk prostate adenocarcinoma. The primary objective of this study is to determine the concordance of imaging findings for fluciclovine-PET/MRI and mpMRI of the pelvis and prostate gland. The secondary objective is to determine the correlation between organ-confined disease, lymph node metastases, extraprostatic extension, and seminal vesicle invasion on fluciclovine-PET/MRI with the expected frequencies of these metastases based on established nomograms and risk-prediction models.

6.2 Sample Size Determination

This is a pilot study that may warrant a larger study with increased power to determine statistical significance if expected results are observed. We plan to enroll 15 patients, primarily determined by budgetary constraints and feasibility of patient recruitment in one year. No formal power calculations were used in the generation of the sample size. The primary end point of the study is to estimate percentage of high-risk prostate cancer patients whose metastasis can be detectable early by using of [¹⁸F]fluciclovine-PET/MRI comparing using standard care of mpMRI imaging. According to risk-prediction models and nomograms used in routine clinical practice, approximately 20-30% of patients with high-risk prostate adenocarcinoma will be diagnosed with nodal metastases. We expect that using [¹⁸F]fluciclovine PET/MRI will achieve similar results, e.g. 30% for early detection of metastasis without invasive procedures, and using mpMRI will result in less of detection of metastasis, e.g. 20%-25%. A size of 15 will provide a two-sided 95% confidence intervals (CI) for point estimate (% of metastasis) from 9.7% to 58.4% when the true estimate is 30% using Clopper-Pearson method. Table below shows the 95% CI when the true estimate varies.

Proportion (%) (estimate of metastasis)	Sample size	95% CI Lower limit	95% CI Upper limit
20	15	4.3	48.1
25	15	6.9	53.4
30	15	9.7	58.4

6.3 Definition of Analyzed Study Population

Study population is adult males with high-risk treatment-naïve prostate adenocarcinoma who meet the inclusion criteria listed above.

6.4 Analysis

Since this is a single arm exploratory pilot study, where no formal power calculations were performed for the study's sample size, this study will largely be exploratory and descriptive. For all clinical and histological evaluations, as well as imaging parameters (SUV), we will generate summary tabulations of the number of observations, mean, standard deviation, median, minimum, and maximum for continuous variables, and the frequency and percentage for categorical variables. Analyses will be primarily descriptive and graphical in nature whereas the proposed sample size for the study limits the distributional assumptions of certain analyses. Therefore, non-parametric approaches will

be considered. For specific aim 1, in order to correlate imaging parameters between imaging modalities our correlation analysis will be performed using Spearman's Rank correlation and Wilcoxon signed-rank sum tests. In order to address specific aim 2, to compare observed frequencies of metastases and expected frequencies, a Chi-squared analysis will be performed. Given the small sample size, a Yates' correction may be utilized. Due to the small sample size and potential for sparse data, we may use Firth's penalized likelihood approach. Data transfer, management, and analyses will be performed using Excel and SAS v9.4.

6.4.1 Analysis for Primary Endpoints and Specific Aim 1: The imaging data from [¹⁸F]fluciclovine PET/MRI or mpMRI will be categorized from 0 to 3 indicating likelihood of having metastasis as '0' indicating no sign of metastasis and >0 indicating there is sign of metastasis. The number and percentage of metastasis identified by either [¹⁸F]fluciclovine PET/MRI or mpMRI will be calculated along with exact 95% CI using Clopper-Pearson method. The agreement and concordance of using these two imaging results will be evaluated with McNemar test due to correlated results from same patients when the result is dichotomized as yes or no, or using Spearman's Rank correlation analysis when the result is measured as 0-3.

6.4.2 Analysis for Secondary Endpoints and Specific Aim 2: Serum prostate-specific antigen (PSA) will be measured for each patient as a clinical risk-predictor as a validated measure to identify PCa and monitor response to treatment. Patients will be identified if they have PCa metastases and response to treatment determined by PSA level (expected) and by using [¹⁸F]fluciclovine PET/MRI (observed) at baseline and 3 months after treatment. To compare observed frequencies of metastases and expected frequencies, a McNemar test will be performed at baseline and 3 month after treatment separately. Further, a generalized estimation equation (GEE) method will be used to examine the association of two diagnosis methods accounting for correlation between baseline and 3 months measurements. Sensitivity, specificity, and accuracy of using [¹⁸F]fluciclovine PET/MRI will be estimated along with 95% CI. Due to the small sample size and potential for sparse data, we may use Firth's penalized likelihood approach. Data transfer, management, and analyses will be performed using Excel and SAS v9.4.

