2.0 Study Objectives

Specific Aim #1: Determine the concordance of imaging findings for fluciclovine-PET/MRI and mpMRI of the pelvis and prostate gland.

Hypothesis #1: Fluciclovine-PET/MRI will identify more regional lymph node metastases than mpMRI alone.

There have been numerous prior studies demonstrating the value of mpMRI for the locoregional staging for PCa. Prior studies in the setting of biochemical recurrence have demonstrated high sensitivity and specificity of fluciclovine-PET/CT for detection of recurrent disease in the prostate bed and extraprostatic disease.¹⁵ We expect the simultaneous acquisition of mpMRI and fluciclovine PET data to provide valuable preoperative staging information, with fluciclovine PET detecting metastatic disease in subcentimeter pelvic lymph nodes not identified with mpMRI alone. Additionally, fluciclovine-PET/MRI provides whole body staging in regions not evaluated by mpMRI and may detect additional distant metastases.

Specific Aim #2: Determine the correlation between organ-confined disease, lymph node metastases, extraprostatic extension, and seminal vesicle invasion on fluciclovine-PET/MRI with the expected frequencies of these metastases based on established nomograms and risk-prediction models as well as follow up fluciclovine-PET/MRI.

Hypothesis #2: Fluciclovine-PET/MRI will demonstrate metastases in the expected frequencies for patients with high-risk PCa and will regress with effective therapy.

For pretreatment patients with PCa, several clinical risk-predictors (including nomograms and Partin tables) utilize serum prostate-specific antigen (PSA), Gleason score, and clinical stage to predict organ-confined disease, the presence of extraprostatic extension, seminal vesicle invasion, and lymph node metastases.² Because majority of the high-risk prostate cancer population in this study will not undergo prostatectomy, nomograms and risk-prediction models combined with follow up fluciclovine-PET/MRI after therapy will be used as a surrogate for accuracy. If successful, this research plan will provide key data for further studies that will use histopathological confirmation as the reference standard.

Specific Aim #3: Measure changes in fluciclovine-PET/MRI at 6-12 weeks after initiation of therapy and correlate with serum PSA.

Hypothesis #3: Fluciclovine-PET/MRI parameters including fluciclovine uptake and fluciclovine-defined metabolic tumor volumes will change with effective therapy.

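### Hypothesis 2 claims agreement with expected frequencies but is analysed with a chi-squared test of difference in 15 men and no agreement margin, so a non-significant result is only weak evidence of a match

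*Combined protocol and SAP*

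**What the plan says.** Section 2.0 states Hypothesis 2 as a claim of agreement: "Fluciclovine-PET/MRI will demonstrate metastases in the expected frequencies for patients with high-risk PCa and will regress with effective therapy". Section 5.1 lists detection in line with model-based frequencies among the primary endpoints. Section 2.0 explains why: most men will not have surgery, so the nomogram comparison, together with the follow-up scan, stands in for accuracy.

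For this aim, section 6.4 says that "to compare observed frequencies of metastases and expected frequencies, a Chi-squared analysis will be performed", and adds: "Given the small sample size, a Yates' correction may be utilized". Section 6.4.2 names a different test, McNemar, for the observed-versus-expected comparison at baseline and at 3 months. Neither section gives a margin, a significance level or a rule for reading the result.

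Section 6.2 supplies the numbers. On sample size: "We plan to enroll 15 patients, primarily determined by budgetary constraints and feasibility of patient recruitment in one year". On power: "No formal power calculations were used in the generation of the sample size". On the nomogram expectation: "approximately 20-30% of patients with high-risk prostate adenocarcinoma will be diagnosed with nodal metastases". On PET/MRI: "We expect that using [¹⁸F]fluciclovine PET/MRI will achieve similar results, e.g. 30% for early detection of metastasis without invasive procedures". It anticipates 20% to 25% for mpMRI.

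The one written decision rule for Aim 2 is in section 4.6.3. Of mpMRI, PET/MRI and their combination, the one whose frequency lies nearest the nomogram's is taken as the most accurate, subject to confirmation in larger studies.

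**The concern.** A chi-squared test of observed against expected counts takes agreement as its null hypothesis. A significant result counts against Hypothesis 2, but a non-significant one shows only that the data were not strong enough to rule agreement out. When the hypothesis of interest is the null itself, a small sample favours it.

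At stake is the surrogate-accuracy conclusion of Aim 2. A scanner that misses most of the expected nodal disease, or over-calls it by half, could often show no significant difference from the nomogram. The optional Yates correction adds to this, because it widens the range of non-significant results and its use is not fixed in advance.

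**Working it through.** **Inputs.** n = 15; expected rate p0 between 20% and 30%; anticipated PET/MRI rate 30% and mpMRI rate 20% to 25% (all section 6.2); chi-squared with optional Yates (section 6.4). Assumptions, because the plan is silent: two-sided 5% level (in line with the two-sided 95% intervals of section 6.2), one result per man, a one-sample test, and the same p0 for every man.

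**1. The plan's own figures.** Clopper-Pearson limits with x = 15p give 4.3 to 48.1% at 20%, 6.9 to 53.4% at 25% and 9.7 to 58.4% at 30%. All three rows of the table in section 6.2 reproduce.

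**2. The test.** With x positive men, X² = (x − 15·p0)² / [15·p0·(1 − p0)] on 1 degree of freedom. Yates reduces |x − 15·p0| by 0.5 before squaring. For x = 0:

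- p0 = 20%: X² = 3²/2.4 = 3.75, p = 0.053. Yates: 2.5²/2.4 = 2.60, p = 0.107.
- p0 = 25%: X² = 3.75²/2.8125 = 5.00, p = 0.025. Yates: 3.25²/2.8125 = 3.76, p = 0.053.
- p0 = 30%: X² = 4.5²/3.15 = 6.43, p = 0.011. Yates: 4²/3.15 = 5.08, p = 0.024.

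Zero detections become significant once p0 exceeds about 20.4% (25.3% with Yates).

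**3. Counts out of 15 that are non-significant.**

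| Expected rate | Uncorrected | Yates |
|---|---|---|
| 20% | 0 to 6 | 0 to 6 |
| 25% | 1 to 7 | 0 to 7 |
| 30% | 2 to 7 | 1 to 8 |

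At 30% the choice of correction alone decides the result for 1/15: X² = 3.5²/3.15 = 3.89, p = 0.049, against 3²/3.15 = 2.86, p = 0.091.

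**4. Chance of a non-significant result when the true rate differs.** This is the Binomial(15, true rate) probability summed over the counts in step 3.

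- Expected 30%, true 10%: P(2 to 7) = 0.45; with Yates, P(1 to 8) = 0.79.
- Expected 30%, true 45%: 0.65; with Yates, 0.82.
- Expected 25%, true 10%: P(1 to 7) = 0.79; with Yates, about 1.00.
- Expected 20%, true 40%: P(0 to 6) = 0.61 with either version.
- Expected 30%, true 20% (the low end anticipated for mpMRI): 0.83; with Yates, 0.96.

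**5. McNemar does not help.** It is also a test of difference. If PET/MRI found nothing and 3, 4 or 5 men were classed as expected-positive, the exact p-value would be 2 × 0.5^k: 0.25, 0.125 or 0.063.

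**6. What agreement would need.** The plan gives no margin, so this is only an illustration. For one-sample equivalence at 5% per side with 80% power and true rate equal to expected, n = p(1 − p)·[(1.645 + 1.282)/margin]². A margin of 20 percentage points needs 35 men at p = 20% and 45 at p = 30%. A margin of 10 points needs 138 and 180.

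**The case against.** The best defence is that the plan does not claim much. It calls itself largely exploratory and descriptive, admits that there was no power calculation, and defers confirmation to larger studies. The closest-match rule in section 4.6.3 ranks point estimates and does not use a p-value. Section 6.4.1 already gives exact intervals for the percentage positive on each modality, and section 6.4.2 adds sensitivity, specificity and accuracy with intervals. Aim 2 also draws on the follow-up scan.

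Part of this stands. A reader might infer that the plan treats non-significance as support for Hypothesis 2; no passage says so. A reader might also infer that the hypothesis would survive even if PET/MRI detected nothing. That is true at an expected 20%, true at 25% only with Yates, and false at 30% with or without Yates under the one-sample test. Nor is the test unable to contradict the hypothesis: at an expected 30% and a true 10%, the uncorrected test rejects 100 − 45 = 55% of the time. The weakness is low power combined with the wrong direction of proof.

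The rest does not remove the point. The closest-match rule says which modality is nearest, not whether any of them matches. The intervals in section 6.4.1 are not set against the nomogram expectation. The exploratory label sits in the same section as the named test, and section 6.2 makes a larger study depend on seeing the expected results.

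**Conclusion.** The concern holds in this limited form: a hypothesis of agreement is paired with a test of difference, without a margin, in a sample where a wide range of results is non-significant. Against an expected 30%, a two-thirds shortfall (true 10%) is non-significant 45% of the time, or 79% with Yates. An excess of half (true 45%) is non-significant 65% of the time, or 82% with Yates. Complete non-detection is missed only towards the low end of the stated 20% to 30% range.

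These figures rest on the assumptions listed with the inputs. Individual nomogram risks in place of one common rate would change the variance slightly. Other forms of the test shift the p-values: a two-sample layout of 0/15 against 4.5/15 gives p = 0.021, or 0.074 with Yates. None of these forms turns a non-significant result into evidence of agreement. The point deserves correction before analysis, but it does not undermine the pilot as a descriptive study.

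**What to change.** In section 6.4 replace the chi-squared test, and in section 6.4.2 the McNemar test named for the same observed-versus-expected comparison, with one estimate. This is O/E: the number of node-positive men divided by the sum of those men's and all other enrolled men's own nomogram probabilities. Give it an exact 95% confidence interval, obtained by multiplying the Clopper-Pearson limits by the number of men and dividing by that sum. Report it for mpMRI, PET/MRI and the combination defined in section 4.6.3. Nomogram risks are pretreatment risks, so this applies to the baseline scan; the 3-month comparison with PSA should be described separately.

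Add two sentences: a non-significant test will not be read as agreement, and 15 men can describe but not confirm a match. The plan's own interval shows why. At 30% it runs from 9.7% to 58.4%, which against an expected 30% is an O/E from 9.7/30 = 0.32 to 58.4/30 = 1.95. If agreement is ever to be claimed formally, in this or a later study, the margin must be fixed beforehand.

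The cost is SAP wording, with no added patients or scans. The downside is a more modest Aim 2 claim.

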Lesion to blood pool and marrow ratios: Tissue SUV is a simple uptake ratio of activity in an area of interest compared to a normalized tissue background level. As stated in section B, activity in lymph nodes measuring less than 1 cm in short-axis dimension will be compared with activity in the blood pool and a lesion:blood pool activity ratio will be calculated. For lymph nodes measuring greater than 1 cm in short-axis dimension, activity will be compared to activity in the L3 vertebral body marrow and a lesion:marrow activity ratio will be calculated..

Dynamic PET analysis: Time-activity curves (TACs) will be generated for pelvic lymph nodes scored as intermediate or high suspicion on visual analysis. Additionally, TACs will be generated for three reference pelvic lymph nodes scored as normal. The maximum SUV at peak fluciclovine uptake, the time to peak, and the shape of the TACs over the 8 min dynamic acquisition (rising, plateau, washout) will be recorded. This analysis is exploratory as the role of dynamic fluciclovine-PET for the initial staging of prostate cancer is not established.

KEY ANALYSIS FOR SPECIFIC AIM 1

Based on the consensus PET and MRI scoring, the total percentage of nodal scoring discrepancies will be calculated. Although the total number of patients is small, a total of 165 pelvic nodal stations will be examined. In this pilot study, a discrepancy between MR-only and fluciclovine-PET/MR greater than 10% would motivate a larger study with more rigorous references standards including histopathology.

KEY ANALYSIS FOR SPECIFIC AIM 2

This study will use the nomograms routinely used by the UAB urology service in assessing newly diagnosed prostate cancer. The use of nomograms is necessary, as we will not routinely obtain histopathological verification in these high-risk, nonoperative patients in this study. Expected frequencies of lymph node metastases based on patient risk factors will be compared to observed frequencies of lymph node metastases in specific aim 1 on mpMRI alone, fluciclovine-PET/MRI, and assuming that discrepant nodes between imaging modalities (i.e. positive on one, negative on other) will be counted as positive, a combination of the two modalities that includes discrepant nodes. The assessment that most closely matches the expected frequency based on the nomogram will be considered most accurate, although small sample size will require larger studies for confirmation.

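### Aim 2 compares observed with expected metastases by chi-squared with an optional Yates correction at 3.0-4.5 expected node-positive men, and sections 6.4 and 6.4.2 disagree on both the test and what 'expected' means

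*Combined protocol and SAP*

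**What the plan says.** All references are to the combined protocol and SAP.

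- **Test in section 6.4.** For Aim 2, "to compare observed frequencies of metastases and expected frequencies, a Chi-squared analysis will be performed". The section adds: "Given the small sample size, a Yates' correction may be utilized". It gives no rule for when the correction applies, no significance level, and no statement of whether the test is one-sample or two-sample.
- **Test in section 6.4.2** (secondary endpoints and Aim 2). "To compare observed frequencies of metastases and expected frequencies, a McNemar test will be performed at baseline and 3 month after treatment separately". Here the expected status of each patient is set by PSA level and the observed status by PET/MRI. No PSA cut-off is given.
- **Source of 'expected' elsewhere.** Section 4.6.3, in the key analysis for Aim 2, says: "Expected frequencies of lymph node metastases based on patient risk factors will be compared to observed frequencies of lymph node metastases", and takes the expected figures from the urology service's nomograms. Sections 2.0 (Aim 2) and 6.1 also refer to nomograms and risk-prediction models.
- **Size.** Section 6.2: "We plan to enroll 15 patients, primarily determined by budgetary constraints", with "approximately 20-30% of patients with high-risk prostate adenocarcinoma will be diagnosed with nodal metastases" as the expected rate. The rate hoped for from PET/MRI is "30% for early detection of metastasis without invasive procedures".
- **How the result is read.** Section 4.6.3 treats whichever of mpMRI, PET/MRI or their combination lies closest to the nomogram frequency as the most accurate, and says larger studies are needed to confirm it. Section 6.4 calls the study largely exploratory and descriptive.

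**The concern.** There are two problems.

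The first is the test. Chi-squared relies on a large-sample approximation, and at 15 men every expected node-positive count in the plan's own range is below the customary minimum of 5. The plan recognises the small sample but leaves the correction open. For some results the p-value then falls on one side of 0.05 or the other according to a choice that the plan does not make.

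The second is the definition. Sections 6.4 and 6.4.2 describe the comparison in almost the same words but name different tests. Read with section 4.6.3, they also use different sources for 'expected': a nomogram in one place, PSA level in the other. An analyst could follow either and report it as the Aim 2 result.

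This matters because most men will have no histology. Section 2.0 uses agreement with the nomogram, together with the follow-up scan, as the surrogate for accuracy, and section 5.1 lists it among the primary endpoints.

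**Working it through.** **Plan's own figure.** The Clopper-Pearson 95% limits in section 6.2 reproduce for n=15 with x = 15p: 20% (x=3) gives 4.33-48.09; 25% (x=3.75) gives 6.86-53.40; 30% (x=4.5) gives 9.74-58.42. The plan prints 4.3-48.1, 6.9-53.4 and 9.7-58.4. The last two use counts that cannot occur, but the arithmetic agrees.

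**Inputs.** n=15 and expected proportion p0 of 20-30% (section 6.2). Assumptions, because the plan is silent: two-sided 5%, in line with its two-sided 95% intervals; a one-sample goodness-of-fit test; one common p0.

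**Expected counts.** 15 × 0.20 = 3.0; 15 × 0.25 = 3.75; 15 × 0.30 = 4.5.

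**Statistic.** With E = 15p0, (|X−E|−c)² × (1/E + 1/(15−E)) is compared with 3.841, where c=0 without correction and c=0.5 with Yates. The actual error rate is the sum of Binomial(15, p0) probabilities over the values of X that reject.

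**At p0 = 30%.**
- Uncorrected: rejects at X≤1 or X≥8. 0.0353 + 0.0500 = 0.0853.
- Yates: rejects at X=0 or X≥9. 0.0047 + 0.0152 = 0.0200.
- Exact binomial (minimum likelihood): same region as Yates, 0.0200.
- Both X=1 and X=8 lie 3.5 from 4.5. Uncorrected: 3.5²/(15 × 0.3 × 0.7) = 12.25/3.15 = 3.889, p=0.049. Yates: 3.0²/3.15 = 2.857, p=0.091.

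**Across the plan's range** (actual error rate, %):

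| p0 | Uncorrected | Yates | Exact binomial |
|---|---|---|---|
| 20% | 1.81 | 1.81 | 1.81 |
| 21% | 5.25 | 2.34 | 2.34 |
| 22% | 5.39 | 2.98 | 2.98 |
| 23% | 5.73 | 1.04 | 3.02 |
| 24% | 6.26 | 1.35 | 2.98 |
| 25% | 3.07 | 1.73 | 3.07 |
| 26% | 3.28 | 3.28 | 3.28 |
| 27% | 3.63 | 3.63 | 3.63 |
| 28% | 4.11 | 1.67 | 4.11 |
| 29% | 4.72 | 1.79 | 4.72 |
| 30% | 8.53 | 2.00 | 2.00 |

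**Width of the peak.** Uncorrected: 5.3% at 29.8%, 8.5% at 29.9%, 8.6% at 30.1%, 5.0% at 30.2%. The peak arises because X=1 and X=8 both only just cross the threshold (z = 1.972 against 1.960). Between the whole-point values, the uncorrected rate below the peak reaches 6.8% (at 24.8%), and Yates runs from 0.9% to 3.8%.

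**Sensitivity at a mean of 30%.** Individual risks spread evenly over 20-40%: 8.2% uncorrected, 1.9% Yates. Over 10-50%: 7.4% and 1.6%. Run instead as a 15-versus-15 two-sample table: 5.5% and 1.5%.

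**The two definitions side by side.** Under section 4.6.3 a nomogram gives each man a probability; the expected count is the sum of those probabilities and is not a second sample. Under section 6.4.2 each man has a PSA-based status and a PET/MRI status, which is paired yes/no data. These are different comparisons with different data structures, yet both are presented as the Aim 2 comparison of observed with expected metastases.

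**The case against.** The strongest reply is that little depends on this p-value. The study is an exploratory pilot with no power calculation, section 4.6.3 judges accuracy by a descriptive closest match, and section 6.4.1 already plans exact Clopper-Pearson intervals for mpMRI and PET/MRI, which can be set against the nomogram figure without any test. Yates, which the plan already offers, has the same rejection region as the exact binomial test at 20% and at 30%. All of this stands, and it limits the weight of the point. It does not settle which test or which definition of 'expected' applies.

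A reader might infer three stronger things that the documents do not support.

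- **That the planned test has an 8.5% error rate.** That figure holds only in a narrow band around 30%. At 20% and 25% neither version exceeds 5%, and at 20% Yates changes nothing. Expected rates will come from each man's risk factors, so the cohort mean need not be 30.0%.
- **That McNemar cannot be run because a nomogram gives only a probability.** Section 6.4.2 does not feed the nomogram into McNemar. It pairs PET/MRI with a PSA-defined status, and McNemar suits paired yes/no data. The fault is the conflicting definition and the missing PSA cut-off.
- **That the correction will be chosen after seeing the data.** The wording leaves this possible. It does not say so.

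**Conclusion.** The point holds as a matter of specification. The nomogram comparison rests on 3.0-4.5 expected node-positive men, an approximate test and a correction with no deciding rule. Sections 6.4 and 6.4.2 give two tests and, with section 4.6.3, two meanings of 'expected' for a comparison described in almost the same words.

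Under a one-sample test at two-sided 5%, the uncorrected error rate is mostly 1.8-6.3% over 20-30%, peaking at 8.5% at about 29.9-30.1%; Yates gives about 1.0-3.6%; the exact binomial test stays at or below 5% throughout. The open choice can change the reading of a result, as with 1/15 or 8/15 at exactly 30%, but it does not do so across the whole range. The counts and rates apply to nodal metastases only, since the plan gives no expected frequencies for the other Aim 2 features.

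The conflict between the sections needs no calculation and no assumption. The practical effect is limited, because no formal decision rests on the test. The change is worth making because nomogram agreement is part of the plan's stand-in for accuracy.

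**What to change.** 1. In section 6.4, replace the chi-squared test and optional Yates correction for the nomogram comparison with one exact test: the number of node-positive men against the sum of the men's individual nomogram probabilities, using the Poisson-binomial distribution. State the significance level and that the test is two-sided.
2. Report observed and expected counts with an exact 95% CI for each of the three assessments in section 4.6.3: mpMRI, PET/MRI and the combination.
3. State in sections 6.4 and 6.4.2 that nomograms define 'expected' for Aim 2, and name the nomogram.
4. Keep McNemar in section 6.4.2 only if a paired PSA versus PET/MRI comparison is still wanted. Label it as a separate analysis and state in advance how PSA is turned into a yes/no status.

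The cost is SAP wording and a short program. No new data are needed, provided that each man's nomogram probability is recorded at baseline from the risk factors that the plan already uses.
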